#### *5.52c Intervention Administration Additional Concerns*

##### Platform Use and Compliance:

- Participants will be instructed to avoid adjusting the platform settings to ensure data is collected. Participants will be contacted if the accelerometers or data collection via the platform is not working properly, or if there are issues with adherence.
- Participants will have access to a research assistant to help resolve technical issues.

**Tracking Devices:**

- The accelerometers assigned to each participant will be tracked according to the product serial number and assigned unique ID number.
- Participants will be allowed to keep the accelerometers as a token of appreciation for their participation in the study, and to minimize potential transmission of skin infections (e.g. methicillin-resistant *Staphylococcus aureus*) between participants.

**5.53 Special Concerns****5.53a Lost Accelerometers**

If a participant reports to study staff that they lost an accelerometer, study staff will provide a replacement, either in person or via mail, as soon as possible.

**5.53b Surveys**

Participants will be contacted in advance to complete their upcoming study survey. After three unreturned voicemails, they will not be contacted again for additional surveys.

**5.54 Compensation**

Ovarian cancer survivors in both arms will receive gift cards valued at \$25 at 14-weeks, and \$50 at 26-weeks if study requirements are completed, including post-baseline assessments and adherence to the accelerometers.

**5.55 Data Security & Privacy**

The data security and privacy of study participants is of utmost importance, and we have taken stringent measures to protect our participants' data. The Penn Medicine Academic Computing Services (PMACS), based out of the University of Pennsylvania, will be the hub for the hardware and database infrastructure that will support the project. The PMACS provides a secure computing environment for a large volume of highly sensitive data, including clinical, genetic, socioeconomic, and financial information. Among the IT projects currently managed by PMACS are: (1) the capture and organization of complex, longitudinal clinical data via web and clinical applications portals from cancer patients enrolled in clinical trials; (2) the integration of genetic array databases and clinical data obtained from patients with cardiovascular disease; (3) computational biology and cytometry database management and analyses; (4) economic and health policy research using Medicare claims from over 40 million Medicare beneficiaries.

All data for this project will be stored on the secure/firewalled servers of the PMACS Data Center, in data files that will be protected by multiple password layers. These data servers are maintained in a guarded facility behind several locked doors, with very limited physical access rights. They are also cyber-protected by extensive firewalls and multiple layers of communication encryption. Electronic access rights are carefully controlled by University of Pennsylvania system managers. Our collaborators at the University of Pennsylvania use highly secure methods of data encryption for all transactions involving participants' financial information using a level of security comparable to what is used in commercial financial transactions. We believe this multi-layer system of data security, identical to the system protecting the University of Pennsylvania Health Systems medical records, greatly minimizes the risk of loss of privacy.

We will take additional steps to minimize the risk of data security breaches by linking individually identifiable health information with participant ID numbers only in a password-protected Excel file that is stored

on Dana-Farber servers, protected by Partners IS infrastructure, and accessible only to members of the study team.

## **5.6 Adverse Reactions and Their Management**

### 5.61 Reporting Adverse or Unanticipated Events

Potential adverse events (AE) for this project are expected to be all non-medical in nature. There is small risk of physical injury. Participants could experience discomfort while wearing the Fitbit on their wrist. Subjects may experience mild anxiety when answering survey questions about emotional issues or questions about coping challenges or difficulties related to discussing the subject matter. The PI will report unanticipated and serious adverse events to the IRB in a timely manner on an ongoing basis. For the purpose of this study a Serious Adverse Event (SAE) is defined as an event that, as a direct result of the study, causes serious harm to the subject (e.g., hospitalization).

### 5.62 Anticipated Reactions & Reaction Management

Should participants become exceedingly upset, disoriented or fatigued or need to attend to matters of personal care during the surveys, study staff will ask the subject if they would like to take a break or reschedule the survey for another time. In the event that participants experience distress while completing surveys, we will follow standard procedures used in our behavioral health intervention studies for counseling and referral. The PI will be notified immediately and participants will be provided with the pager numbers for both the study PI and the study psychiatrist included in the consent form. [name], a DFCI psychiatrist, has agreed to serve as a psychiatrist on the study. [name] will evaluate any participants who are distressed for risk of imminent danger and refer them to appropriate services if they are needed.

## **6.1 Primary and Secondary Endpoints**

### **Primary Endpoints**

- 1) *Preliminary Analysis:* To assess the feasibility, acceptability and perceived effectiveness of the accelerometer + social support + gamification intervention in 20 ovarian cancer patients and their partners.
- 2) *Final Analysis:* To compare the change in daily steps from baseline to the 14-week intervention period between the intervention arm and control arm.

### **Secondary Endpoints**

#### *Preliminary Analysis:*

- 1) Comparing the change in daily steps from baseline to the 14-week and 26-week intervention periods.
- 2) Comparing the change in quality of life (EuroQol EQ-5D index) and symptoms of anxiety and depression at baseline, 14 and 26 weeks.
- 3) Comparing additional clinical and quality-of-life outcomes including functional capacity (6-minute walk test), symptom burden (NFOSI-18), fear of recurrence (ASC) and others, at baseline, 14 and 26 weeks.

#### *Final Analysis:*

- 1) Comparing the change in daily steps from baseline to 26 weeks between the intervention arm and control arm.
- 2) Comparing the change in quality of life (EuroQol EQ-5D index) and symptoms of anxiety or depression (HADS) at 14 and 26 weeks between the intervention arm and control arm.
- 3) Comparing health care utilization at 14 and 26 weeks between the intervention and control arm.
- 4) Comparing additional clinical and quality-of-life outcomes including functional capacity (6-minute walk test), symptom burden (NFOSI-18), fear of recurrence (ASC) and others, at 14 and 26 weeks between the intervention and control arm.

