### Final Analysis (RCT with 148 ovarian cancer survivors and 74 partners)

Objective: To evaluate the effectiveness of a modified game-based intervention designed to enhance social incentives in increasing physical activity relative to control.

- Hypothesis: The game-based intervention will increase physical activity at 14 weeks compared with a wearable device.
- Hypothesis: The relative differences in activity between groups will persist at 26 weeks.

Objective: To evaluate the effectiveness of a game-based intervention designed to enhance social incentives in improving ovarian cancer survivors' quality of life and mental health relative to control.

- Hypothesis: Participants in the game-based intervention arm will report significantly better quality of life and lower rates of anxiety or depression at 14 and 26 weeks, compared to those with a wearable device.

A preliminary analysis will be conducted after the 20-patient run-in of the intervention. The final analysis will take place after all patients have completed the study. The final analysis will exclude patients from the run-in phase, since this group of patients will not undergo randomization.

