### *Final Analysis*

148 patients will be randomized 1:1 to one of the two arms – accelerometer only, or accelerometer + gamification + social support. For the outcome of change in steps, we will compare the change in daily steps from baseline to the 14-week T1 time point between the intervention arm and control arm to conclude that the intervention is promising for further study. We use 1000 steps as our threshold for powering statistical significance, which for the average person is about half a mile. A priori power calculations assumed a baseline mean step count of 6000 steps in the control group with a standard deviation of 2000 steps, a 15% dropout rate, and a 2-sided  $\alpha$  of 0.05. It was estimated that a sample of 148 participants (74 per arm) would ensure 80% power to detect a 1000 step difference between the gamification + social support and control arms in the change in mean daily steps from baseline to the maintenance phase.

Fitness tracker	Gamification / social support	Arm	Sample size
+	-	1 (Accelerometer only)	74
+	+	2 (Accelerometer + gamification + social support)	74
		Total	148

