#### 6.3b Final Analysis (74 patients in each arm)

**Change in steps:** The primary outcome will be the change in participants' daily step counts from baseline to the end of the 14-week intervention period. A secondary outcome will be the change in participants' daily step counts from baseline to the 26-week follow-up period.

**Quality of life:** A secondary outcome will be the change in the participants' quality of life from the baseline to 14- and 26-week follow-up periods, as assessed with the NIH-funded Patient Reported Outcome Measure Information System (PROMIS)-29 scale.

**Mental health:** Another secondary outcome will be the change in the participants' symptoms of anxiety and depression from the baseline to 14- and 26-week follow-up periods, as assessed by the Hospital Anxiety and Depression Scale (HADS).

Additional clinical and QoL outcomes: We will assess changes in additional clinical and quality of life outcomes, including functional capacity (6-minute walk test), symptom burden (NFOSI-18), fear of recurrence (ASC) and others, at 14 and 26 weeks between the intervention and control arm.

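### The randomized quality-of-life and mental-health objective is worded as a significance claim, but the plan names two rival quality-of-life instruments, two visits and an open outcome list, with no error control

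*Combined protocol and SAP*

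**What the plan says.** **The claim.** The second objective of the randomized trial (2.0, Final Analysis) is that intervention participants "will report significantly better quality of life and lower rates of anxiety or depression at 14 and 26 weeks". It names no instrument and gives neither visit priority.

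**The measures.**
- 6.1 (Secondary Endpoints, Final Analysis, item 2) ties quality of life to the EQ-5D index and mental health to HADS, at 14 and 26 weeks.
- 6.3b names PROMIS-29 for quality of life instead. Section 5.21g keeps six of its subscales (physical function, fatigue, sleep disturbance, social roles, pain interference, pain intensity) and names no summary score.
- 6.3b analyses HADS as change in "symptoms of anxiety and depression from the baseline to 14- and 26-week follow-up periods", whereas 2.0 speaks of rates. Section 5.21b gives a cut-off of 8. Nothing says whether anxiety, depression or the total score is tested.
- 6.1 item 4 adds the 6-minute walk, NFOSI-18 and "fear of recurrence (ASC) and others, at 14 and 26 weeks between the intervention and control arm". Section 6.3b repeats the open ending. Both describe these as clinical and quality-of-life outcomes.

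**Error control.** The "2-sided $\alpha$ of 0.05" in 6.2 belongs to the power calculation for steps. Sections 6.1 to 6.3 give no adjustment, testing order, key secondary endpoint or exploratory label for the randomized comparisons. Such labels are used for the run-in, which is descriptive in 6.2 and has exploratory quality-of-life and mental-health outcomes in 6.3a.

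**The concern.** A hypothesis stated in terms of significance needs a rule for deciding whether it has been met. Here quality of life alone can be read from seven scores (EQ-5D plus six PROMIS-29 subscales) at two visits. HADS adds more scores and an undecided coding, and the additional list has no end.

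Participants know whether they have a partner and game features, and most of these outcomes are self-reported in interviews run by a research assistant. If instrument, visit and coding can be settled after the data are seen, a quality-of-life or mental-health benefit could be reported with a false-positive risk well above the nominal level, and a reader could not tell which comparison had been intended.

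**Working it through.** **1. The plan's own figure.** Inputs from 6.2: "We use 1000 steps as our threshold for powering statistical significance"; "with a standard deviation of 2000 steps"; "a 15% dropout rate"; "2-sided $\alpha$ of 0.05"; 80% power.
- n per arm = 2 × [(1.960 + 0.842) × 2000 / 1000]² = 62.8.
- 62.8 / 0.85 = 73.9, so 74 per arm and 148 in total.

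The stated sample size reproduces. It covers one comparison, steps at 14 weeks. No error rate is stated for the secondary endpoints.

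**2. Counting the tests for the objective in 2.0.**

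| Set | Scores × visits | Tests |
|---|---|---|
| A: 6.1 item 2 | (EQ-5D, HADS anxiety, HADS depression) × 2 | 6 |
| B: quality of life only, 6.1 and 6.3b | (EQ-5D, six PROMIS-29 subscales) × 2 | 14 |
| C: A plus PROMIS-29 | 9 × 2 | 18 |

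None of these counts the 6-minute walk, NFOSI-18, ASC, utilization, 26-week steps or the unnamed others.

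**3. Chance of at least one false positive.** Assumptions, since the documents give no figures: no true effect, each test two-sided at 0.05, and a common correlation ρ among test statistics. For independent tests the chance is 1 − 0.95^k in either direction and 1 − 0.975^k in the favourable direction. For k = 6 these are 1 − 0.735 = 0.265 and 1 − 0.859 = 0.141. Correlated cases come from simulating equicorrelated normal statistics.

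| Set | k | ρ = 0 | ρ = 0.5 | ρ = 0.7 | Favourable only, ρ = 0 / 0.5 / 0.7 |
|---|---|---|---|---|---|
| A | 6 | 26% | 21% | 16% | 14% / 10% / 8% |
| B | 14 | 51% | 35% | 25% | 30% / 17% / 12% |
| C | 18 | 60% | 40% | 28% | 37% / 20% / 14% |

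**4. The strict joint reading.** Read literally, the hypothesis in 2.0 requires better quality of life and lower anxiety or depression together. Suppose this needs a favourable result on a quality-of-life score at either visit and on HADS anxiety or depression at either visit.
- EQ-5D as the only quality-of-life score: (1 − 0.975²) × (1 − 0.975⁴) = 0.049 × 0.096 = 0.5% if independent, rising to about 2.5% at ρ = 0.7.
- PROMIS-29 subscales also admitted: (1 − 0.975¹⁴) × (1 − 0.975⁴) = 0.298 × 0.096 = 2.9% if independent, and about 5% at ρ = 0.5 to 0.7.

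The inflation therefore attaches to separate claims about quality of life or about mental health, which 6.1 and 6.3b set up as separate outcomes.

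**The case against.** Several stronger readings are tempting, and the documents do not support them.

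- **That the hypothesis rests on the open list.** It does not. 6.1 item 2 anchors it to EQ-5D and HADS, and the open list is a separate item of additional outcomes. The boundary is blurred only because that item is also said to hold quality-of-life outcomes.
- **That a false positive is likely.** A reader who counts every named secondary comparison (27, including steps, utilization and the walk test) gets 1 − 0.95^27 = 75%. That needs independence, and it includes outcomes outside this objective. At correlations of 0.5 and 0.7 the same count gives about 48% and 33%. For the six tests in 6.1 item 2 the figure never exceeds 27%.
- **That any nominal p below 0.05 would meet the hypothesis.** Direction matters, and so does the word joining quality of life to mental health. On the joint reading the error is about 0.5-5%.
- **That HADS will be analysed as rates.** Only 2.0 uses that word. 6.1 and 6.3b both analyse change in symptoms.

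It is also fair to say that 5.1 calls the final scale scores preliminary estimates, that 6.2 aims to show promise for further study, and that labelling all secondary outcomes exploratory would be an acceptable alternative.

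What remains is that 5.1 also says effectiveness on quality of life and mental health will be assessed, 2.0 speaks of significance, the two sections name different instruments, and no rule or label is given.

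**Conclusion.** The point holds in limited form. The plan does not say which quality-of-life score, which HADS score or which visit decides the objective, and it sets no error control. With two-sided 0.05 per test and correlations of 0 to 0.7, all assumed, the chance of at least one false positive is about 16-27% for EQ-5D plus the two HADS scores (8-14% favourable). With the PROMIS-29 subscales it is 28-60% (14-37% favourable). It passes one half only for the wider sets under weak correlation. The length of the open list is unknown, so it is not in these figures. The single primary comparison keeps its 5% error rate. This is a cheap improvement to the plan and does not threaten the trial's main conclusion.

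**What to change.** 1. **Reconcile 6.1 and 6.3b** by naming one quality-of-life score. If PROMIS-29 is chosen, state which single subscale or summary is meant. State which HADS score is used (anxiety, depression or total), analysed as mean change.
2. **Define three key secondary tests:** steps at 26 weeks, the chosen quality-of-life score at 14 weeks and the chosen HADS score at 14 weeks. Interpret them only if the primary is significant, with Holm adjustment at two-sided 5%. The ordered p-values are compared with 0.05/3 = 0.0167, 0.05/2 = 0.025 and 0.05, stopping at the first that fails.
3. **Replace the open ending** in 6.1 and 6.3b with a closed list. Report every other score and visit as an estimate with a 95% confidence interval and no significance claim.
4. **Align the hypothesis in 2.0** with this: same instrument, same visit, and change in score in place of rates.

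Cost: wording in 2.0, 6.1 and 6.3b, with no extra patients, visits or data. The downside is that outcomes outside the key set, including quality of life and mental health at 26 weeks, cannot be called significant.

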## **6.2 Sample Size and Statistical Power or Precisions**

### *Preliminary Analysis*

A convenience sample of 20 ovarian cancer survivors and 20 partners will be enrolled for the run-in portion of the study. Due to the limited sample size, statistical analysis will be descriptive in nature.

### *Final Analysis*

148 patients will be randomized 1:1 to one of the two arms – accelerometer only, or accelerometer + gamification + social support. For the outcome of change in steps, we will compare the change in daily steps from baseline to the 14-week T1 time point between the intervention arm and control arm to conclude that the intervention is promising for further study. We use 1000 steps as our threshold for powering statistical significance, which for the average person is about half a mile. A priori power calculations assumed a baseline mean step count of 6000 steps in the control group with a standard deviation of 2000 steps, a 15% dropout rate, and a 2-sided  $\alpha$  of 0.05. It was estimated that a sample of 148 participants (74 per arm) would ensure 80% power to detect a 1000 step difference between the gamification + social support and control arms in the change in mean daily steps from baseline to the maintenance phase.

Fitness tracker	Gamification / social support	Arm	Sample size
+	-	1 (Accelerometer only)	74
+	+	2 (Accelerometer + gamification + social support)	74
		Total	148

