### 5.34 Intervention

On Day 0, patients receiving the intervention will be given two wearable accelerometers, and the study's research assistant will explain to them how to use the devices. Participants will select a family member or friend to enhance social incentives by motivating the individual towards her goal by participating in the intervention with them, so the patient will be asked to give the second fitness to a partner with whom she will participate in the study. After recording their steps passively for 2 weeks, patients will be asked to set a step goal to increase with their partner. The step goal should be of 33% to 50% higher than baseline or to choose their own goal (minimum  $\geq 1500$  steps greater than baseline). Ovarian cancer survivors and their partners will sign a pre-commitment contract agreeing to try their best to achieve their daily step goal, which helps to motivate behavior change. Participants will also receive an exercise prescription (Appendix E) which has been recommended in the care of midlife and older women and aims to motivate exercise behavior change.

At the start of each week, participants receive 70 points (10 for each day). Points are endowed to leverage loss aversion – a concept from prospect theory that reveals that individuals are more motivated by losses than gains. Each day participants are informed of their step count. If the step goal was achieved, they keep the points. However, each day the goal is not met, they are informed that they lost 10 points. Points are replenished at the start of the week to leverage the “fresh start effect.” Participants will be offered the opportunity to move up or down “levels” within the platform. At the end of the week, if the participant has  $\geq 40$  points, she will advance up one level. Levels include: blue (lowest), bronze, silver, gold, platinum (highest). If she has  $< 40$  points, she will drop down one level. This creates a sense of achievable goals (goal gradients) and longer-term loss aversion.

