**5.52 Intervention Administration*****5.52a Intervention Administration Overview***

The intervention will begin the day that a participant receives an accelerometer and enrolls in the study on the Way to Health platform. See the protocol schema for details.

**Control Arm:** Participants assigned to the control arm will receive a wearable accelerometer and be enrolled in the Way to Health platform on "day 0." They will be asked to wear the wearable accelerometer daily for 14 weeks. Patients in the control arm will not receive social support or gamification in the Way to Health platform. Research assistants will be in contact with patients to resolve any technical issues they may be having and to address issues of nonadherence. At approximately 14 weeks after study enrollment, patients will be asked to complete a follow-up interview (T1), be moved out of the "active intervention" phase and enter into the follow-up phase. During the follow-up phase, research assistants will be accessible for questions about technical issues. At approximately 26 weeks after study enrollment, patients will complete a second follow-up interview (T2) and their participation in the study will end.

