#### Intervention

- *Intervention Arm Only:* After recording their steps passively for 2 weeks, participants will be asked to set a step goal to increase with their partner. The step goal should be of 33% to 50% higher than baseline or to choose their own goal (minimum  $\geq 1500$  steps greater than baseline). Study staff will ask patients and partners to fill out a pre-commitment contract agreeing to try their best to achieve their daily step goal, which helps to motivate behavior change. Participants will also be given an exercise prescription.

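### Section 6.3b names no model for the primary change-in-steps comparison; adjusting 14-week steps for baseline steps would raise power under either reading of the 2000-step SD, except where the baseline/14-week correlation is high

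*Combined protocol and SAP*

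**What the plan says.** **Outcome and analysis.** Section 6.1 gives the final-analysis primary endpoint as "To compare the change in daily steps from baseline to the 14-week intervention period between the intervention arm and control arm". Section 6.3b gives it as change in "daily step counts from baseline to the end of the 14-week intervention period". Neither section names a test, a model or a covariate, and no other section does.

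**Power.** Section 6.2 (Final Analysis) states: "A priori power calculations assumed a baseline mean step count of 6000 steps in the control group with a standard deviation of 2000 steps". It adds 15% dropout, two-sided alpha of 0.05, 80% power, a 1000-step difference and 74 patients per arm. It gives no SD of change and no correlation between baseline and follow-up steps.

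**Follow-up time.** Section 6.2 says "we will compare the change in daily steps from baseline to the 14-week T1 time point between the intervention arm and control arm", but its power sentence refers to a difference "in the change in mean daily steps from baseline to the maintenance phase". The term maintenance phase is not defined and appears nowhere else.

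**Baseline.** For the intervention arm, section 5.34 says "After recording their steps passively for 2 weeks, patients will be asked to set a step goal to increase with their partner", with the goal set relative to baseline; section 5.52b repeats this. Section 5.52a says "The intervention will begin the day that a participant receives an accelerometer and enrolls in the study on the Way to Health platform". Section 5.33 gives no baseline step window for controls, although section 5.3 has steps monitored passively in both arms.

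**The concern.** Steps are measured at both ends in the same women, so the choice between an unadjusted change score and a baseline-adjusted comparison affects precision. Under randomization, with a baseline that arm has not influenced, both estimate the same between-arm difference. In large samples the adjusted one is never less precise, and it also accounts for chance imbalance at baseline. Leaving the model open gives up that precision, or leaves the choice to be made after data are seen.

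The SD matters for the same reason. The SD of steps at one time and the SD of change are different quantities, linked by a correlation that the plan does not give. If 2000 really is a baseline SD, the power of a change-score analysis depends on that correlation.

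**Working it through.** **Inputs from section 6.2:** difference 1000, SD 2000, two-sided alpha 0.05, power 80%, dropout 15%, 74 per arm.

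**Reproducing the plan's figure.** n per arm = 2 × (1.960 + 0.8416)² × (2000/1000)² = 62.8. Dividing by 0.85 gives 73.9, so 74 per arm and 148 in total. Evaluable patients are 74 × 0.85 = 62.9 per arm. Power is 80.1% by the normal formula and 79.5% by the noncentral t. The stated size therefore follows if 2000 is the SD of whatever is compared.

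**Formulas.** Let s0 and s1 be the SDs of steps at baseline and 14 weeks, and ρ their correlation.

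- SD of change = √(s0² + s1² − 2ρ·s0·s1)
- Residual SD after baseline adjustment = s1·√(1 − ρ²)

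Power is by noncentral t with 62.9 per arm; the adjusted model spends one more degree of freedom. The documents give no ρ, so 0.3, 0.5 and 0.7 are assumptions.

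**Reading A: 2000 is the SD of steps at both times.** SD of change = 2000·√(2(1 − ρ)); residual SD = 2000·√(1 − ρ²).

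| ρ | SD of change | Residual SD | Change score | Adjusted |
|---|---|---|---|---|
| 0.3 | 2366 | 1908 | 65% | 83% |
| 0.5 | 2000 | 1732 | 79% | 89% |
| 0.7 | 1549 | 1428 | 95% | 97% |

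Here the change score reaches 80% only if ρ is about 0.5 or more.

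**Reading B: 2000 is the SD of change, with equal SDs at both times.** Residual SD = 2000·√((1 + ρ)/2).

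| ρ | Residual SD | Change score | Adjusted |
|---|---|---|---|
| 0.3 | 1612 | 79% | 93% |
| 0.5 | 1732 | 79% | 89% |
| 0.7 | 1844 | 79% | 85% |

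**Where the gain runs out.**

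- Reading A at ρ = 0.8: 99.3% against 99.6%, so almost nothing is left to gain.
- Reading B at ρ = 0.9: 79.5% against 81.4%.
- In general the two SDs coincide when ρ = s0/s1. With s0 = 2000 and s1 = 2250, that is ρ = 0.889, and both SDs are 1031.

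**Unequal SDs.** With s0 = 2000, s1 = 2250 and ρ = 0.3, power is 60% for the change score and 74% adjusted. Adjustment still helps, but it does not guarantee 80% if the 14-week SD exceeds 2000.

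**Baseline timing.** Section 5.34 has intervention patients receive a second tracker for a partner on Day 0, so arm is already known by then. The 2-week recording comes afterwards. In the readable text (the schema figure is not shown), this baseline may therefore be post-randomization.

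**The case against.** - **The sample size is right.** A reader might infer from the baseline wording of the SD that the trial is undersized. The documents do not support that: 148 reproduces, and 2000 may have been meant as the SD of change.
- **A change score is valid, and nothing excludes adjustment.** Both are true. The plan names no model, so the unadjusted change score used as comparator is an assumption, though the 148 is consistent with it. The case is for a better method, not against an invalid one.
- **The gain rests on assumed correlations.** This stands. Stopping at 0.7 favors adjustment, and at 0.8 and above Reading A shows almost no gain.
- **The time points conflict less than they seem to.** Sections 5.52a and 5.52b place T1 at about 14 weeks, when the active phase ends. So the T1 time point in 6.2 and the end of the 14-week period in 6.3b are the same. Only the looser wording in 6.1 and the maintenance phase in 6.2 need reconciling.
- **Defining windows does not itself raise power in any computable way.** This also stands. The gain shown comes from the covariate; windows fix what is being estimated.
- **Adjustment does not rescue a contaminated baseline.** If arm or partner involvement shifts steps during the first two weeks, the change score and the adjusted estimate are both biased. The remedy has to acknowledge this.

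**Conclusion.** The point holds as an improvement that costs almost nothing, not as an error in the sample size or an invalid analysis. No primary model is named, and the one SD given is ambiguous. With 62.9 evaluable per arm, a 1000-step effect and equal SDs, adjustment adds about 18, 10 and 2 percentage points at correlations of 0.3, 0.5 and 0.7 if 2000 is the SD of steps. It adds about 14, 10 and 6 points if 2000 is the SD of change. The correlations are assumptions, and the gain vanishes as the correlation nears the baseline SD divided by the 14-week SD. The precision argument also presumes a baseline unaffected by arm, which the readable text does not secure.

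**What to change.** **Section 6.3b.** Make the primary analysis a linear model of 14-week mean daily steps on arm, with baseline mean daily steps as covariate, reporting the adjusted difference with its 95% CI. Use the same form for 26-week steps. Define one baseline window, identical in both arms and ending before goals and gamification start, and state which days are averaged at 14 weeks. Acknowledge that this baseline may be post-randomization, and add a sensitivity analysis, for example one using the earliest recorded days as baseline.

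**Section 6.2.** Say what 2000 is the SD of, and show power over an assumed range of correlations and of 14-week SDs on both sides of 2000.

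**Sections 6.1 and 6.2.** Reconcile the 14-week intervention period and the maintenance phase with the 14-week T1 time point.

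**Cost.** Wording and one degree of freedom. Steps are already recorded passively in both arms, so no extra patients, visits or data are needed.
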